## **4 Statistical methods**

All analyses use SAS® version 9.4 or higher. Summary tables will be organized by each dose level; if some dose levels have few patients, then dose levels could be combined into dose ranges. All available data will be used in the analyses, and important data will be included in data listings, sorted by dose level, patient, and by visit within patient. Missing data will not be imputed, except via censoring in survival analyses and as otherwise specified.

Unless otherwise noted, categorical data will be presented using counts and percentages, with the number of patients in the analysis set by treatment group as the denominator for percentages. Percentages will be rounded to one decimal place, except 100% will be displayed without any decimal places and percentages will not be displayed for zero counts. Continuous data, unless otherwise noted, will be summarized using the number of observations (n), mean, standard deviation (std), median, minimum, and maximum. Minima and maxima will be rounded to the precision of the original value, and means, medians, and 95% confidence intervals (CIs) if presented will be rounded to 1 decimal place greater than the precision of the original value. The std will be rounded to 2 decimal places greater than the precision of the original value, up to a maximum of 3 decimal places.

No hypothesis testing will be performed in this study.

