3.1 Study Design

This is a Phase 1, open-label, dose escalation (Part 1) and expansion (Part 2) study of the safety and tolerability of ADCT-402, used as monotherapy, in patients with relapsed or refractory B-cell NHL. The study will determine the MTD, as well as evaluate the preliminary activity, PK, pharmacodynamics, and other exploratory assessments of ADCT-402.

Patients will receive a 1-hour intravenous (IV) infusion of ADCT-402, at escalating doses, on Day 1 of each cycle. If ADCT-402 is well tolerated after the first cycle, the infusion duration may be shortened to 30 minutes for subsequent cycles for that patient, at the Investigator's discretion.

For each patient, the study will include a screening period (up to 28 days), a treatment period (until withdrawal, [Section 4.2](#)), and a follow-up period to assess disease progression and survival for up to 12 months after the last dose of study drug. The total study duration will depend on overall patient tolerability to the study drug and response to treatment. It is anticipated that the duration of the entire study (Parts 1 and 2) could be approximately 3 years from first patient treated to last patient completed.

Part 1

In Part 1, patients will be assigned to treatment according to a 3+3 dose escalation design ([Section 3.2](#)) and oversight of a Dose Escalation Steering Committee (DESC) ([Section 6.3.1.1](#)).

During the conduct of Part 1, and prior to implementation of Amendment 5, alternative dosing schedules are being evaluated at the discretion of the DESC as described below:

- 120 µg/kg: Dosing every 3 weeks for 2 cycles. Patients with at least SD after the second cycle continue treatment at a reduced dose of 60 µg/kg q6weeks, beginning 6 weeks after Cycle 2 infusion.
- 150 µg/kg: Dosing every 3 weeks for 2 cycles. Patients with at least SD after the second cycle continue treatment at a reduced dose of 60 µg/kg q6weeks, beginning 6 weeks after Cycle 2 infusion.
- 200 µg/kg: Dosing every 6 weeks for 2 cycles. For patients with at least SD 6 weeks after Cycle 2, continue treatment at a reduced dose of 60 µg/kg q6weeks, beginning 6 weeks after Cycle 2 infusion.
- 200 µg/kg: Dosing every 6 weeks. For patients with at least SD 6 weeks after Cycle 1, continue treatment at a reduced dose of 60 µg/kg every 6 weeks beginning 6 weeks after Cycle 1 infusion.

Changes described in part 2 resulted from requests based on DESC decisions.

Part 2

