In Part 2, (expansion), patients will be assigned to the recommended dose level(s) and schedule(s) of ADCT-402 identified in Part 1 based on evolving safety, efficacy and pharmacokinetic data.

The *population* in Part 2 expansion may be restricted to specific histologies based on both signals of activity and the safety observed in Part 1.

Further, *dose levels and schedules* evaluated in Part 2 may include but are not limited to the following:

- A. **90, 120, 150, and/or 200 µg/kg:** Dosing every 3 weeks.
- B. **120 µg/kg:** Dosing every 3 weeks for 2 cycles. Patients with at least SD after the second cycle continue treatment at a reduced dose of 60 µg/kg q6weeks, beginning 6 weeks after Cycle 2 infusion.
- C. **150 µg/kg:** Dosing every 3 weeks for 2 cycles. Patients with at least SD after the second cycle continue treatment at a reduced dose of 60 µg/kg q6weeks, beginning 6 weeks after Cycle 2 infusion.
- D. **200 µg/kg:** Dosing every 6 weeks for 2 cycles. For patients with at least SD 6 weeks after Cycle 2, continue treatment at a reduced dose of 60 µg/kg q6weeks, beginning 6 weeks after Cycle 2 infusion.
- E. **200 µg/kg:** Dosing every 6 weeks. For patients with at least SD 6 weeks after Cycle 1, continue treatment at a reduced dose of 60 µg/kg every 6 weeks beginning 6 weeks after Cycle 1 infusion.

The continuation of each patient's treatment will be based on an independent verification of local response assessments, unless otherwise approved by the sponsor.

The DESC will determine and document the dose levels, schedules, and disease subtypes to be evaluated in Part 2. These determinations by the DESC will be provided in writing.

Based on emerging safety and efficacy profile, the DESC may add additional cohorts to part 2 of the study with the same or different dosing regimens and for the same or different B-cell NHL histologies. The dose will not exceed the highest dose tested in part 1 at which 3 patients cleared the DLT observation period.

Patients who discontinue treatment for any reason other than disease progression will continue to be followed approximately every 12 weeks from the last disease assessment until disease progression, or initiation of new anticancer treatment.

After documentation of disease progression or start of new treatment, patients will be followed (by telephone contact or chart review) approximately every 12 weeks for up to 12 months after the last dose of study drug to collect survival information.

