5.3 Treatments Administered

In Part 1 (dose escalation), each patient will be assigned a dose level and schedule as described in [Section 3.1](#) and [Section 3.2](#). In Part 2 (expansion), all patients will be assigned to the recommended dose level(s) and schedule(s) of ADCT-402 identified in Part 1 by the DESC.

ADCT-402 will be administered on Day 1 of each cycle as a 1-hour IV infusion. If ADCT-402 is well tolerated after the first cycle, the infusion duration may be shortened to 30 minutes for subsequent cycles, on an individual patient basis, at the Investigator's discretion. Variations in infusion times due to minor differences in IV bag overfill/underfill and the institution's procedure for flushing chemotherapy lines will not result in protocol deviation.

Prophylactic antiemetic medications, electrolyte supplementation, and other standard supportive care measures may also be administered according to standard treatment center protocols, or as in [Section 5.2](#) and [Section 5.9.2](#).

Although the study patient population has a low risk for development of tumor lysis syndrome (TLS) compared to patients with acute disease ([Cairo, 2010](#)), patients should be observed for development of TLS and treated according to standard treatment center protocols.

Because of non-clinical observations related to nephropathy, adequate patient hydration (e.g., 8 to 10 glasses of water or equivalent per day) is recommended for patients receiving ADCT-402.

Additionally, because new or worsening edema and / or new or worsening pleural effusion have been observed, patients are advised to monitor their weight on a daily basis ([Section 6.3.8](#) and [5.9.2](#))

As non-clinical testing indicates testicular toxicity (atrophy with reduced spermatogenesis), male patients are advised to consider cryopreservation of sperm prior to treatment with ADCT-402, where applicable.

Available pre-clinical data on ADCT-402 does not suggest a photosensitivity concern, based on the lack of any signals in the rat and monkey toxicology studies with ADCT-40

However, skin rash has been reported in the ADTC 402-101 study, as well as with another investigational agent containing the same pyrrollobenzodiazepine warhead (Rudin, 2016). The rash has been limited to areas at risk for sun exposure, it is therefore recommended that precautions are taken to avoid prolonged exposure of skin to direct sunlight.

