### 3 Study Design

This is a Phase 1, open-label, dose escalation (Part 1) and expansion (Part 2) study of the safety and tolerability of ADCT-402, used as monotherapy, in patients with relapsed or refractory B-cell NHL. The study will determine the MTD, as well as evaluate the preliminary activity, PK, pharmacodynamics (PD), and other exploratory assessments of ADCT-402.

In Part 1, patients will be assigned to treatment according to a 3+3 dose escalation design and oversight of a Dose Escalation Steering Committee (DESC). The initial dose of ADCT-402 will be 15 µg/kg (Dose Level 1), and the highest allowed dose will be 300 µg/kg. The dose-limiting toxicity (DLT) observation period for dose escalation is 1 cycle. Patients will be entered sequentially to each dose level. No intra-patient dose escalation is allowed. During Part 1, the DESC may expand enrollment at any dose level in which 3 patients have completed the DLT observation period if at least 1 patient in the study has achieved a partial response (PR) or better, or if further evaluation of PK or PD data is deemed necessary to characterize pharmacology in humans. No more than 10 patients in total can be treated at any dose level unless  $\geq 3$  of the 10 patients have achieved a PR or better.

In Part 2, (expansion), all patients will be assigned to the dose level(s) of ADCT-402 identified in Part 1. During dose expansion, patients will be monitored for safety using the same DLT criteria employed during dose-escalation. If during the treatment period, >30% of patients experience safety events that would meet the criteria that define a DLT in the dose-escalation phase of the study, enrollment in the expansion cohort(s) may be paused and the study data reviewed to determine whether additional monitoring or other action (such as alternate dose levels) should be evaluated prior to further enrollment.

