#### 3.3 Modifications to the statistical section of the protocol

The efficacy analysis set was defined in the protocol as all patients with valid baseline data who receive at least 2 doses of study drug or who have documented progression of disease at any time after the first dose of study drug. However, a few patients received 200 µg/kg on an every 6 weeks (Q6W) schedule and their disease assessments were performed before the second dose. These patients should be considered as evaluable for efficacy analysis.

Therefore, the efficacy analysis set is updated in the SAP to include all patients who have received at least one dose of ADCT-402 with a valid baseline and at least one valid post-baseline disease assessment or patients who have documented progression of disease or death at any time after the first dose of study drug.

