#### **4.7 Exposure to Treatment**

##### **4.7.1 Extent of ADCT-402 Exposure**

ADCT-402 exposure will be summarized for the safety analysis set by dose level. Duration of treatment, total number of cycles dosed, total dose received (in  $\mu\text{g}$  and  $\mu\text{g}/\text{kg}$ ), and average dose per cycle (in  $\mu\text{g}$  and  $\mu\text{g}/\text{kg}$ ) will be tabulated. When actual weight adjusted dose is needed, the last available weight before each infusion will be used. Dose administered at each infusion ( $\mu\text{g}$ ) is calculated by concentrated IP volume (in mL)\* 5 mg/mL \*1000 or serially diluted IP volume (in mL)/50\* 5 mg/mL \*1000; for partial infusion, multiply by (1-volume of dosing solution not administered [in mL]/ 50 mL).

Dose delays and dose reductions could also be analyzed if relevant. A cycle is delayed if it starts more than 3 days post- scheduled date.

Exposure data and infusion details will be listed together.

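### The SAP groups results by dose level (µg/kg) although patients are assigned a dose level and a schedule, so one group can pool regimens whose planned dose before week 12 differs up to 3.1-fold

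*SAP*

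**What the plan says.** **Assignment.** Protocol 5.3 says that in Part 1 "each patient will be assigned a dose level and schedule as described in" protocol 3.1 and 3.2. For Part 2, protocol 3.1 says "patients will be assigned to the recommended dose level(s) and schedule(s) of ADCT-402 identified in Part 1". It adds that "the DESC may add additional cohorts to part 2 of the study with the same or different dosing regimens".

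**Regimens.** Protocol 3.1 lists regimens A to E for Part 2, without limiting Part 2 to them. B to E were already under evaluation in Part 1.
- A: 90, 120, 150 and/or 200 µg/kg every 3 weeks.
- B and C: 120 or 150 µg/kg every 3 weeks for two cycles, then 60 µg/kg every 6 weeks, starting 6 weeks after the Cycle 2 infusion.
- D: 200 µg/kg every 6 weeks for two cycles, then 60 µg/kg every 6 weeks.
- E: 200 µg/kg, described as "Dosing every 6 weeks. For patients with at least SD 6 weeks after Cycle 1, continue treatment at a reduced dose of" 60 µg/kg, starting 6 weeks after Cycle 1.

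Table 1 of the protocol defines a dose level by µg/kg alone.

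**Analysis.** SAP 4 states: "Summary tables will be organized by each dose level; if some dose levels have few patients, then dose levels could be combined into dose ranges". Later sections repeat the grouping. SAP 4.7.1 says "ADCT-402 exposure will be summarized for the safety analysis set by dose level", and 4.8.2.1 (adverse events), 4.9.1 (ORR), 4.9.2 (DOR), 4.9.4 (PFS) and 4.9.5 (OS) also present results by dose level. SAP 3 describes Part 2 without the schedule: "all patients will be assigned to the dose level(s) of ADCT-402 identified in Part 1". The SAP does know of the schedules. Section 3.3 widens the efficacy set because a few patients received 200 µg/kg "on an every 6 weeks (Q6W) schedule and their disease assessments were performed before the second dose".

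**The concern.** The unit of assignment is a regimen; the unit of tabulation is a dose. SAP 3.3 settles that the every-6-week patients count as evaluable, but nothing settles which table group they belong to. Under the stated rule they join any patients given the same µg/kg every 3 weeks.

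The study has to determine the recommended dose(s) for Part 2, a primary objective, and Part 2 then assigns dose and schedule together. A reader of the report will want the safety and activity of a regimen. A group averaged over schedules gives a mixture whose weights are set by how many patients happened to be enrolled on each. The option to merge sparse dose levels into dose ranges would allow further mixing across schedules.

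**Working it through.** The documents give no planned cumulative dose, so there is no stated figure to reproduce.

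**Inputs.** Doses and intervals come from protocol 3.1. The patient is assumed to stay on treatment with at least stable disease, without delay or toxicity-related reduction.

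**Formula.** Planned dose before week 12 = sum of all doses scheduled at weeks t < 12.

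| Dose group | Regimen | Doses (week) | Planned µg/kg |
|---|---|---|---|
| 200 | A, every 3 weeks | 200 (0, 3, 6, 9) | 4 × 200 = 800 |
| 200 | D | 200 (0, 6) | 2 × 200 = 400 |
| 200 | E | 200 (0), 60 (6) | 200 + 60 = 260 |
| 150 | A, every 3 weeks | 150 (0, 3, 6, 9) | 4 × 150 = 600 |
| 150 | C | 150 (0, 3), 60 (9) | 300 + 60 = 360 |
| 120 | A, every 3 weeks | 120 (0, 3, 6, 9) | 4 × 120 = 480 |
| 120 | B | 120 (0, 3), 60 (9) | 240 + 60 = 300 |

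**Ratios within a group.**
- 200 µg/kg: 800/260 = 3.08 and 800/400 = 2.00.
- 150 µg/kg: 600/360 = 1.67.
- 120 µg/kg: 480/300 = 1.60.

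**Sensitivity to the counting rule.** Counting a dose due exactly at week 12, the 200 µg/kg regimens plan 1000, 460 and 320 µg/kg, and 1000/320 = 3.13. Both conventions round to 3.1.

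**Sensitivity to the horizon.** Before week 3 the three 200 µg/kg regimens are identical. Before week 6, A plans 400 µg/kg and D and E plan 200 (2.0-fold), while B and C still match continuous dosing. The A/E ratio is 1200/320 = 3.75 at 18 weeks and 1600/380 = 4.21 at 24 weeks.

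**Disease assessment.** Under protocol 6.1, both schedules are scanned at about 6 and 12 weeks. After that, continuous every-3-week patients are scanned every third cycle (3 × 3 = 9 weeks), and patients on a 6-week schedule at least every 12 weeks. A dose-level PFS or DOR curve can therefore also pool two intervals for detecting progression.

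**What a pooled rate estimates.** If regimen r has share w_r of the group and true rate p_r, the group rate is Σ w_r × p_r. It equals a regimen's own rate if the p_r are all equal or if one regimen fills the group. The documents give no w_r beyond the remark about a few patients, and no p_r, so the shift cannot be calculated.

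**The case against.** **The SAP may leave room for schedule.** SAP 4 and 4.8 use the term treatment group, and the subgroup clauses in 4.8, 4.9.1 and 4.9.2 are open-ended. The SAP is also to be read with the protocol. But the visible text never defines treatment group as a regimen, the subgroup analyses are optional and do not name schedule, and the sections that specify tables say dose level. This room permits the right analysis without securing it.

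**The numbers may be small and the listings sufficient.** With only a few every-6-week patients, the shift could be minor, and the dose and infusion listings would let a reader separate them by hand. This stands as a limit on importance. It would stand less well if the committee opened Part 2 cohorts on different schedules at one dose, which the protocol allows.

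**The tables do not choose the regimen.** The steering committee does so on emerging data and records it in writing, and no formal interim analysis is planned. This stands: the point concerns what the report can show.

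**Stronger readings that the documents do not support.**
- A reader might infer that the exposure tables hide the difference. SAP 4.7.1 also tabulates treatment duration and total dose received.
- A reader might infer that a DLT rate at 200 µg/kg would mix 21-day and 42-day windows. SAP 4.8.1 only lists DLTs, and although protocol 7.6.1.1 names a DLT summary, it sets no dose-level layout. No section states a 42-day window; protocol 5.1 and footnote 23 of the schedule of procedures describe 21-day cycles.
- A reader might infer that the 18-day redosing rule among the SAP's protocol deviations misses early redosing on a 6-week schedule. It is given as an example, and the surrounding text is incomplete in the available copy.

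**Conclusion.** The point holds as a gap between assignment and tabulation. By the SAP's stated rule, a dose group can pool regimens with planned doses before week 12 of 800, 400 and 260 µg/kg (200 µg/kg), 600 and 360 (150 µg/kg), or 480 and 300 (120 µg/kg). These are planned doses for a patient who continues, and the ratios depend on the horizon. Mixing at 120 and 150 µg/kg, or of every-3-week with every-6-week dosing at 200 µg/kg, requires that patients were in fact treated on both. The SAP confirms only that some received 200 µg/kg every 6 weeks.

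The effect on reported rates and curves is unknown. A reader might infer that pooling would make 200 µg/kg look safer than 150 µg/kg, or that an MTD or committee decision was wrong. Neither follows: the first needs enrolment shares and dose-risk relations that the documents do not give, and nothing in them bears out the second. This is an inexpensive improvement to a descriptive analysis, worth making before the tables are produced.

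**What to change.** In SAP 4, define the analysis group as the assigned starting regimen, meaning dose level plus schedule: A to E of protocol 3.1, with A split by dose, and any regimen that the committee adds. Use that group in 4.7.1, 4.8.2.1 and 4.9.1 to 4.9.5. In addition:
- Keep a dose-level total as a secondary column.
- List, rather than tabulate, a regimen with very few patients.
- Do not combine dose ranges across schedules.
- Add received dose per week to the exposure summary in 4.7.1.

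**Cost.** SAP wording and extra table columns. The assigned regimen must be known to treat the patient, and infusion details are already recorded, so no new procedure is needed. Cells become smaller and confidence intervals wider. In a study without hypothesis tests, that is an acceptable price for results that refer to a regimen patients received.

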### **4.1 Analysis Sets**

#### **4.1.1 Safety Analysis Set**

The safety analysis set consists of all patients who receive ADCT-402.

#### **4.1.2 DLT-evaluable Analysis Set (Part 1)**

The DLT-evaluable analysis set consists of patients who complete one cycle of ADCT-402. The patients with completed DLT information will be included even if they discontinue early, before the end of cycle 1.

#### **4.1.3 Efficacy Analysis Set**

The efficacy analysis set consists of patients who receive at least one dose of ADCT-402 with a valid baseline and at least one valid post-baseline disease assessment or patients who have documented progression of disease or death at any time after the first dose of study drug and before the start of any subsequent anticancer therapy or procedure.

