4.1.11 Long-term Follow-up

Patients who discontinue treatment for any reason other than objective disease progression will continue to be followed with scans approximately every 12 weeks from the last tumor assessment until disease progression, or initiation of new anticancer treatment. If a patient discontinues treatment for a hematopoietic stem cell transplant, the frequency of imaging will be as per the transplant center standard of care.

After documentation of disease progression or start of new treatment, patients will be contacted by telephone approximately every 12 weeks for up to 12 months after the last dose of study drug to collect survival information.

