#### **4.8.2.2 Deaths**

The following deaths summaries will be generated on the safety analysis set.

- Number (%) of patients who died during the study and reasons for death
- Number (%) of patients who died within 30 days after last dose of study drug except deaths occurred after taking any subsequent anticancer therapy/procedure and reasons for death

All deaths will be listed.

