#### **4.9.5 Overall Survival**

Overall survival is defined as the interval between the date of first dose and the date of death from any cause. Patients who are known to be alive as of their last known status will be censored at their date of last contact. Patients who are lost to follow-up will be censored at the date the patient is last known to have been alive. The last confirmed alive date is the latest of the following: study visit date, telephone contact date, end of study last confirmed alive date, follow-up systemic (anticancer) therapy end date or start date (if ongoing or end date is missing), local or central radiologist scan date, or other date in the clinical database.

OS will be estimated and displayed by dose levels for the efficacy analysis set using Kaplan-Meier methods (SAS® PROC LIFETEST). A Kaplan-Meier plot will be presented.

The results of all peripheral white blood cell populations, DNA cross-link formation, and renal functional tests will be listed by patient.

[Redacted content]

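### Overall survival is estimated in an efficacy set whose membership, for unscanned patients, depends partly on dying or progressing before new therapy; SAP 3.3 and 4.1.3 also define that set differently

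*SAP*

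**What the plan says.** - **OS population.** SAP 4.9.5 starts the clock at first dose and counts death from any cause. It then states: "OS will be estimated and displayed by dose levels for the efficacy analysis set using Kaplan-Meier methods". No OS analysis in all treated patients is planned. Protocol 7.6.2.3 defines OS without naming an analysis set; Protocol 7.6.2.4 names the efficacy population for progression-free survival.
- **Who is in the efficacy set.** SAP 4.1.3 gives two routes. One is a valid baseline plus at least one valid post-baseline assessment. The other is documented progression or "death at any time after the first dose of study drug and before the start of any subsequent anticancer therapy or procedure". SAP 4.9 accepts clinical progression from the end-of-treatment or disposition page, so progression need not be seen on a scan.
- **The same set in SAP 3.3.** The section that explains the change from the protocol gives the second route as "documented progression of disease or death at any time after the first dose of study drug", with no new-therapy limit.
- **Survival data after new therapy.** Protocol 4.1.11 covers those who have progressed or begun another therapy: "patients will be contacted by telephone approximately every 12 weeks for up to 12 months after the last dose of study drug". The purpose of these calls is survival follow-up. SAP 4.9.5 lists "follow-up systemic (anticancer) therapy end date or start date (if ongoing or end date is missing" among its last-alive dates.
- **An all-treated set exists.** SAP 4.1.1: "The safety analysis set consists of all patients who receive ADCT-402". SAP 4.8.2.2 already uses it: "The following deaths summaries will be generated on the safety analysis set".

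**The concern.** OS needs no scan, so a missing post-baseline assessment is no reason to leave a treated patient out of it. For unscanned patients, the set makes inclusion depend on what happens next. Early death brings a patient in. Reaching new therapy alive and without documented progression keeps the patient out, and a later death does not reverse that under 4.1.3. A curve built this way does not describe the survival of everyone who was treated. Its denominator also differs from that of the death summaries, which use the safety set.

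The mismatch between 3.3 and 4.1.3 adds to this. Two programmers working from the two sections could build different sets from the same data. They would differ precisely on deaths, which are the OS events. With Part 2 cohorts of about 10 to 20 patients (Protocol 7.3), one or two such patients can visibly move a curve.

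**Working it through.** The documents give no OS figure, so there is none to reproduce. The check has four steps.

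**1. Classify treated patients with no valid post-baseline assessment.**

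| Course | SAP 4.1.3 | SAP 3.3 | All treated |
|---|---|---|---|
| Dies before new therapy | in | in | in |
| Progression documented (including clinical) before new therapy, whatever follows | in | in | in |
| No documented progression, starts new therapy, then dies | **out** | **in** | in |
| No documented progression, no recorded death (alive or lost) | out | out | in |

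The third row is the contradiction between the two sections.

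**2. Can such patients occur?** The screening scan may be up to 28 days before Day 1 (Protocol 4.1.1). Appendix 12.1.1, footnote 25, puts the end-of-treatment visit within 30 days of the last dose. A scan is required at that visit only if the last assessment was more than 9 weeks (63 days) earlier (Protocol 4.1.9).
- One dose: at most 28 + 30 = 58 days, below 63, so no end-of-treatment scan is required.
- Two doses three weeks apart: up to 28 + 21 + 30 = 79 days, above 63, so a scan can be triggered.

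After treatment, patients without progression are "followed with scans approximately every 12 weeks from the last tumor assessment until disease progression, or initiation of new anticancer treatment". The main affected group is therefore patients who leave after one dose and start new therapy before a follow-up scan. Protocol 4.1.9 dates the visit from treatment discontinuation rather than last dose; on that reading the interval can be longer and the group smaller.

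**3. Direction of the error.** Under 3.3, no excluded patient has a recorded death. Adding such patients to a Kaplan-Meier analysis adds only censored times. Each factor is 1 − d/n, with d deaths among n at risk. The additions leave d unchanged and can only raise n, so no factor falls. The estimate in the set is thus equal to or below the all-treated estimate. Under 4.1.3 some excluded patients have died, so the error can go either way.

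**4. Size, on assumed inputs.** Let u be the excluded share and s the survival of excluded patients at a fixed time, with complete follow-up and 50% survival in the set:

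S(all) = (1 − u) × 0.50 + u × s, with s between 0 and 1

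- u = 5%: 0.95 × 0.50 = 0.475, up to 0.475 + 0.05 = 0.525.
- u = 10%: 0.90 × 0.50 = 0.45, up to 0.45 + 0.10 = 0.55.

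Worked cohort of 20, also assumed. Seventeen are scanned, of whom 8 are alive at 12 months; the other 9 die at months 2.5, 3, 4, 5.5, 6, 7, 8, 9.5 and 11. Unscanned patient A dies at month 2 before new therapy. Unscanned B and C start new therapy and never have documented progression. Where they die, B dies at month 5 and C at month 8. Kaplan-Meier OS at 12 months:

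| B and C | SAP 4.1.3 | SAP 3.3 | All treated |
|---|---|---|---|
| B dies, C alive | 8/18 = 44.4% | 8/19 = 42.1% | 9/20 = 45.0% |
| Both die | 44.4% | 8/20 = 40.0% | 8/20 = 40.0% |
| Both alive | 44.4% | 8/18 = 44.4% | 10/20 = 50.0% |
| Both lost at month 1 | 44.4% | 44.4% | 44.4% |
| Both lost at month 3 | 44.4% | 44.4% | 17/20 × 8/15 = 45.3% |

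The 4.1.3 figure does not respond to B and C at all. The all-treated figure runs from 4.4 points below it to 5.6 points above it. Early loss to follow-up hardly matters; recorded outcomes after new therapy do.

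**The case against.** The strongest case against is that the group is very small. Clinical progression counts, so many early leavers are kept without a scan. The one-dose timing depends on dating the end-of-treatment visit from the last dose. Dose delays do not move the scan schedule (Protocol 6.1), and off-treatment patients without progression are scanned about every 12 weeks. Exclusion criterion 1 bars patients who, at entry, have any other treatment option in the investigator's opinion, which makes early new therapy less likely. The excluded share is assumed, and the worked cohort uses the top of the assumed range (2 of 20). The shifts it shows are small beside the exact 95% interval for 8/18, which is 21.5% to 69.2%. The safety-set death summaries, the death listing and a planned listing of derived OS data (SAP 4.9, population not stated) soften the effect further. SAP 3.3 also has a sound motive: the protocol's two-dose rule would have left out evaluable patients on six-weekly dosing.

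All of this stands, and it limits the severity. It does not remove the dependence on outcome or the contradiction between 3.3 and 4.1.3. The death summaries and listings give no estimate of survival over time in all treated patients.

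A reader might infer three stronger things that the documents do not support:
- That every unscanned patient other than an early death is dropped, or that every unscanned patient who dies after new therapy is. Documented progression before new therapy keeps a patient in under both wordings.
- That under 3.3 everyone excluded is a survivor. They have no recorded death; some may be lost or withdrawn. The one-way result concerns the Kaplan-Meier estimate, not true survival.
- That the plan inflates OS. Under 4.1.3 the error can go either way.

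**Conclusion.** The point holds, and it is minor. OS in the efficacy set leaves out unscanned patients with neither documented progression nor death before new therapy, although the plan collects their survival and an all-treated set is already defined. SAP 3.3 and 4.1.3 disagree on those who later die, and that disagreement needs settling however few they are.

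The size cannot be derived from the documents. The 45–55% range assumes 10% excluded, complete follow-up and 50% survival in the set, and its ends require every excluded patient to have died or to be alive; the likely effect is smaller. OS is a secondary endpoint and SAP 4 plans no hypothesis testing, so no formal conclusion turns on it.

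**What to change.** - In SAP 4.9.5, make the safety analysis set (all treated patients) the OS population, and keep OS in the efficacy set as a sensitivity analysis. Nothing in the protocol conflicts with this.
- Make SAP 3.3 and 4.1.3 agree on whether progression or death must come before subsequent anticancer therapy.
- Optional and lesser: add an overall response rate in all treated patients, counting unassessed patients as non-responders. It may come out slightly lower. For example, with 7 responders among 20 treated, 2 of the others unassessed, the rate is 7/20 = 35.0% against 7/18 = 38.9% with those 2 removed.

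The cost is SAP wording and a few extra tables; no new data are needed.
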